6.0 MEASUREMENT OF EFFECT

All scales have good psychometric properties with similar populations. Listed below are the factors to be measured and measurement instruments.

Intake only. Study staff will confirm patient eligibility via patients' UW Qualtrics screening surveys . Patients report demographics (biological sex, race, ethnicity, age, education).

Protocol
HS IRB #2019-0337
Version 5. 10/17/19
Version 6. 04/07/20
Version 7. 10/09/20
Version 8. 01/26/21
Version 9. 08/18/21
Version 10. 07/13/23

Drinking and quality of life. Patients will be asked to take surveys administered via the Tula app (see Table 1 for frequencies). Patients will be asked to report on their drinking using the 7-day timeline follow-back^{58,59} survey. Patients will also take the PROMIS Global Health⁶⁰ survey (10 items) to assess patient self-reported quality of life and a modified version of the Brief Alcohol Monitor⁶³ survey (10 items) to assess their risk and protection factors for problematic alcohol use. Alcohol use disorder severity (AUD scale,⁶⁴ 11 items; AUDIT, 10 items; 7-day timeline followback, 5 items) will be assessed at baseline and once every 3 months.

Mediators. Self-determination theory constructs will be assessed (see Table 1 for frequencies) via the Tula app as follows:

- Competence – Perceived Competence Scale (4 items)
- Relatedness – CHESS Bonding Scale^{65,66} (5 items)
- Autonomous motivation – revised Treatment Self Regulations Questionnaire⁶⁷ (6 items)

Tula use. Tula use is collected in time-stamped log files and includes when a patient accessed Tula, the services used, duration of service use, pages viewed, messages posted and received, and content of messages. Tula use will be used to measure dose of intervention received for dose/response analyses. Patients will be asked to take a survey about their value of Tula at baseline and 12 months.

Healthcare utilization. Healthcare utilization will be collected from the self-reported medical services utilization form⁶¹ (6 items; see Table 1 for frequency).

Intervention and implementation costs. Intervention costs will be determined using Tula time-stamped log files and billing codes logged by the health coach. Implementation costs will be determined through clinic staff interviews at the end of the intervention period. Cost per patient will be determined for each study group (self-monitored, peer-supported, and clinically integrated) with intervention and implementation costs separated within each group.

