Site Staff: Up to 20 staff from participating UW Health clinics will be recruited to participate in interviews to provide feedback on the implementation of Tula. Interviews will take place with two distinct groups of staff:

1. Primary care clinicians are from a clinic that had at least 10 patients enroll in the clinically integrated group; and
2. Clinicians who participated in interviews during the development year.

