Clinically integrated group. In addition to receiving the same static content available to all patients, patients in the clinically integrated group will also have access to a discussion group with others in the group (like the peer-supported group described above) and access to a health coach from the UW Health Wellness Center. Health Coaching at UW Health's Center for Wellness at the American Center is provided by a Certified Wellcoach, either in-person at the American Center or over the phone. Health Coaching sessions are not scheduled via Health Link: Health Coaches directly and independently manage their own client calendars. Patients schedule a session directly with the Health Coach via phone or email. When the Health Coach sees a client for more than one session, they schedule the first session via phone or email, then set up subsequent sessions during the first session. Standard clinical Health Coach appointments are not documented in any way in Health Link, nor will they be for this study; as an out-of-pocket, open-to-the-public service, The Center for Wellness uses an independent third-party system, ActiveNet, for any billing needs.

Patients will be encouraged to participate in up to three in-person or phone visits with the health coach at the beginning, middle, and end of the active 90-day implementation period, with the first visit lasting between 60 and 90 minutes and the other two lasting between 20 and 45 minutes. The health coach will also function as the moderator of the discussion group, as the peer mentor does in the peer-supported group.

Patients will have the option to share selected Tula data with the health coach through a dashboard. When a patient in this group completes a survey, they will be presented with a question: "Do you want to share your responses with the health coach? Yes/No." If the subject responds "yes," their survey responses will populate a dashboard that contains data on drinking days / drinks per day and other data reported via the weekly survey. The health coach will have the option to view the data in the dashboard. Data in the dashboard will not be placed in the patient subject's electronic medical record. However, if the health coach sees any data that is concerning that would normally prompt follow-up within the scope of their clinical role, the health coach will contact and follow-up with the patient subject if such a situation were to arise.

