The UW Health Coach at the American Center is not professionally obligated to communicate with a patient's PCP; in most coaching circumstances, the Health Coach would not know the identity of a patient's PCP, and having an established relationship with a PCP is not a prerequisite for inclusion in

Protocol

HS IRB #2019-0337
Version 5. 10/17/19
Version 6. 04/07/20
Version 7. 10/09/20
Version 8. 01/26/21
Version 9. 08/18/21
Version 10. 07/13/23

the study or health coaching in general. That said, there may be circumstances where action/communication may be warranted if a subject discloses information that has a direct bearing on his or her health. The Wellness Center has several primary care providers on site at the American Center that the health coaches involved in this study routinely consult in such circumstances.

This sensitive health information being collected and shared through the Tula dashboard allows the coaches to be better informed and provide more responsive treatment. Information shared via the dashboard serves only to support the intervention and will not be used as study data; no response is expected of the health coach relative to her research role. Health coach communication with a patient in the course of the intervention will be dependent on the individual health coaching plan the patient creates with the support of the health coach in accordance with the Whole Health model used by the health coach. If a patient declines to share data to the dashboard, no data will be transmitted to the dashboard.

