To schedule the first of three coaching visits, which may take place on-site at the UW Health Center for Wellness or via phone conversation, the health coach will use the private messaging feature in Tula. Subsequent visits may be scheduled during that first 60-90 minute visit or via the app's private messaging feature, depending on the patient's preference. During the consult, the health coach will review "What Matters to Me," the Wellness Center survey patients complete during the run-in period. The health coach will work with the patient to form a vision of what their health could be by asking the patient "What do you want your health *for*? ", helping the patient develop a short-term goal, and formulate an action plan. Following the initial coaching session, the patient may use Tula to journal about their experiences so they can refer to this information during brief weekly or bi-weekly follow-up encounters with the health coach, which will take place via private message over Tula, and/or during their two subsequent health coaching visits. The health coach will ask patients how they are doing, how they are progressing toward their goals, where they want to go from here, and how they want to get there. The health coach will provide structure for the patient to achieve their self-identified goals.

Clinic staff. Clinic staff will be asked to participate in interviews in a private room at their clinic. The study team will interview two groups of clinicians: 1) the primary care clinicians who the team interviewed in the developmental year and 2) clinicians at clinics that have had at least 10 patients (in the clinically integrated group) using Tula. Interviews will take place once the intervention phase of the study is complete. Clinic staff subjects will be informed of the study and sign an informed consent. Subjects will be reminded that their participation is voluntary, that they do not need to answer any questions they do not want to answer, and that they may leave the interview at any time. The study team will ask open-ended questions about the implementation process of Tula such as what barriers to implementation the clinic experienced, what worked well, and what can be improved upon for next time. Clinicians will also be asked the "Iowa A-CHESS value for clinic managers" survey. The interview will be recorded and transcribed by a member of the study team. During transcription all names will be coded and any identifying information will be removed.

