Protocol

HS IRB #2019-0337
Version 5. 10/17/19
Version 6. 04/07/20
Version 7. 10/09/20
Version 8. 01/26/21
Version 9. 08/18/21
Version 10. 07/13/23

External Research Site and Personnel

Safe Communities of Madison–Dane County is a local non-profit [501(c)(3)] coalition that brings together public and private sector partners to save lives, prevent injuries, and make the community a safer place. The organization focuses on projects and programs with a track record of positive impact and success and has been involved with research projects and initiatives at UW–Madison and UW Health since its inception in 1999. As a community partner for this study, Certified Peer Specialists employed by Safe Communities will provide in-app peer mentoring and discussion forum monitoring/moderation for the study arm receiving the peer-supported intervention. Certified Peer Specialists recognized in the State of Wisconsin complete peer support training, examination, and continuing education requirements specific to both mental health and substance use-oriented lived experiences. Safe Communities of Madison–Dane County is accredited under guidelines established by the World Health Organization Collaborating Center on Community Safety Promotion, National Safety Council's Safe Communities America Network and Pan Pacific Network of Safe Communities.

Data collection.

Table 1 shows the data collection for the study, including source, burden, and timing.

Table 1: Quantitative Outcomes

Dimension	Measure	Source	Burden	Timing (after rand.)
Patient Outcomes				
Risky drinking patterns	Timeline followback ^{58,59}	Patient survey	5	0, 3, 6, 9, 12 mo.
Quality of life	PROMIS Global Health ⁶⁰	Patient survey	10	0, 3, 6, 9, 12 mo.
Willingness to share data	Number of participants opting to share Tula data with clinicians	Tula	NA	Continuous
Cost				
Healthcare utilization	Medical services utilization form ⁶¹	Patient survey	4	0, 6, 12 mo.
Implementation costs	Clinician experience with implementation of Tula.	Staff interview	60 min.	Once, after the intervention is complete.
Other Outcomes				
Risk/protection factors	Brief Alcohol Monitor ⁶³	Patient survey	10	0, 3, 6, 9, 12 mo.
Specialist report use (clinicians)	Number of days used	Server log files	NA	Continuous
Alcohol use severity	AUDIT	Patient survey	10	
AUD severity	DSM-5 ⁶⁴	Patient survey	11	Pretest, 12 months

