Quarterly follow-up surveys. Starting at month 3, patient subjects will be asked to take surveys once every 3 months. The study team will ask patient subjects to take the following surveys: 1) quality of life, 2) a modified version of the brief alcohol monitor, 3) timeline follow-back, 4) CHESS bonding scale, 5) alcohol competence scale, 6) TSRQ, 7) medical services utilization (6 months and 12 months only), 8) AUD severity (12 months only), 9) value of Tula (12 months only), 10) quality of life and 11) AUDIT. Two additional questions related to the impact of COVID-19 on participants' physical and mental health will be added to the quality of life measures. These questions will operate on a 5-point Likert scale and will be included across all CHESS studies. (See supporting document "4.6.20 Global Health Scale v1.3_COVID.docx").

Use data. The app automatically collects use data by placing "cookies" on subjects' smartphones (with patients' consent) when randomization takes place. Data are stored on a secure central server at CHESS.

Qualitative interviews. In order to better understanding the implementation of Tula in the health coaching and peer mentoring organizations, the study team will use the CFIR framework to interview the two health coaches and four peer mentors, as well decision makers in these organizations. In order to better understand the conditions under which Tula can be sustained, the team will conduct interviews with organizational decision makers and health system decision makers. Sample questions for each of these interviews are shown below. Interviews will take place at month 36 and last 30-60 minutes. Members of the research team who have received training in qualitative interviewing will conduct the interviews. Interviews will be conducted via a secure video conference call (Zoom) and will be audio recorded. Participant identities will be protected. Any identifiers will be coded in the transcripts so that there will be no way to link clinicians to their interview responses. Data collected will be used to refine the system for future dissemination.

Protocol

HS IRB #2019-0337

Version 5. 10/17/19

Version 6. 04/07/20

Version 7. 10/09/20

Version 8. 01/26/21

Version 9. 08/18/21

Version 10. 07/13/23

For health coaches and peer recovery workers	Sample Implementation Questions
CFIR Domain	

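### Implementation cost is to be taken from primary care clinicians, who do not deliver Tula; the people who deliver it are interviewed, but their interviews are not linked to cost

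*Combined protocol and SAP*

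**What the plan says.** Section 6.0 (Intervention and implementation costs) splits cost in two. Intervention cost comes from app log files and the health coach's billing codes. For the other part: "Implementation costs will be determined through clinic staff interviews at the end of the intervention period". It also requires a per-patient cost for all three groups, with the two parts kept separate within each. Table 1 in Section 5.0 gives the implementation-cost measure as "Clinician experience with implementation of Tula", from one 60-minute staff interview.

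Section 3.0 (Site Staff) lists two kinds of interviewee. One is given as "Primary care clinicians are from a clinic that had at least 10 patients enroll in the clinically integrated group; and"; the other, drawn from earlier work, is given as "Clinicians who participated in interviews during the development year". Section 4.0 repeats these groups, and Section 5.0 (Clinic staff) describes them as "1) the primary care clinicians who the team interviewed in the developmental year and 2) clinicians at clinics that have had at least 10 patients"; the count of 10 refers to patients of the coached arm.

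Section 5.0 also describes who runs the supported arms. The clinically integrated arm is run by a health coach from the UW Health Wellness Center. On records: "Standard clinical Health Coach appointments are not documented in any way in Health Link, nor will they be for this study". On contact with the patient's own provider, in most coaching circumstances "the Health Coach would not know the identity of a patient's PCP". The peer-supported arm is run by certified peer specialists employed by a community non-profit.

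Separately, under Qualitative interviews, Section 5.0 says that "the study team will use the CFIR framework to interview the two health coaches and four peer mentors, as well decision makers in these organizations". These interviews take place at month 36, and health-system decision makers are interviewed too.

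**The concern.** Implementation cost is what it takes to set an arm up and keep it running: training, set-up, supervision and moderation. The people who can report it are those who did the work or paid for it. The plan instead names a group whose described part in the trial is mainly to recommend it to patients.

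Cost matters in this trial. The introduction aims to find the most cost-effective implementation strategy. Section 8.0 (Intervention analyses) lists cost among the primary outcomes, and its Operational cost analysis plans an incremental cost-effectiveness ratio (ICER) of the clinically integrated against the peer-supported group. If the stated rule is followed, one of the two cost components has no informed source in either of those arms.

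**Working it through.** The plan gives no implementation-cost figure to reproduce, so the check sets the stated source beside the stated roles.

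**1. Who is asked.** Sections 3.0, 4.0 and 5.0 agree on the two clinician groups. Health coaches and peer mentors are not among them; they appear only under Qualitative interviews.

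**2. Who does the work.**

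| Arm | Delivered by | Clinicians' described part |
|---|---|---|
| Clinically integrated | Wellness Center health coach, who also moderates the discussion group | Recommending the study (4.0); primary care providers on the coach's site may be consulted (5.0) |
| Peer-supported | Peer specialists from an outside non-profit | Recommending the study |
| Self-monitoring | App alone, with messages to the research coordinator | Recommending the study; regular care continues |

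**3. What the clinicians can see.** Coaching visits are not entered in Health Link. Section 5.0 also keeps dashboard data, and all data collected by Tula, out of the medical record. A patient need not have an established primary care provider to take part.

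**4. What they are asked.** The topics listed for the clinician interview are barriers, what worked, possible improvements and a value survey. No time or resource item is listed. The sample questions for coaches, peer mentors and decision makers cover their roles, supports, barriers and organisational fit. They too list nothing on hours, training time or resources. The stated use of those interviews is to refine the system; no section links them to cost. The bibliography holds a method for mapping implementation resources (entry 62), but Table 1's implementation-cost row names no instrument.

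**5. Effect on a cost comparison.** Let I_C and I_P be the true implementation costs of the clinically integrated and peer-supported arms, and r_C and r_P the amounts the clinicians report. Each arm has 546/3 = 182 patients. If implementation cost is included, the error in incremental cost per patient is

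[(r_C − r_P) − (I_C − I_P)] / 182.

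If the clinicians report little for either arm, this is about −(I_C − I_P)/182. Incremental cost is then understated when the coaching arm was dearer to set up and overstated when the peer arm was. The documents give neither quantity, so the sign is unknown.

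**6. Scale.** As a unit conversion and not an estimate, a net gap of 100 hours in either direction is 100/182 = 0.55 hours, about 33 minutes of staff time per patient.

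**The case against.** The strongest reply is that the protocol does not depend on primary care clinicians alone. It interviews coaches, peer mentors and decision makers in both organisations, and asks what they did and what stood in the way. That stands. A reader might infer that the integration and cost aims cannot be answered at all, and the documents do not support that. The delivery-side interviews serve the integration aim, intervention cost has its own sources, and health-care use comes from patient surveys. Only the implementation-cost component is affected.

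Second, the protocol uses the word clinician loosely. Table 1 speaks of sharing data with clinicians when the recipient is the health coach, so its implementation-cost row might be meant to include coaches. That is possible, but Section 6.0 says clinic staff, and Section 5.0 defines clinic staff without them. The interview questions are also labelled as samples, so the full guides may hold more. Neither point makes the link to cost that is missing from the text.

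Third, Section 8.0 does not say whether implementation cost enters the ICER. This is correct, and the effect on the ICER is therefore conditional.

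Fourth, clinicians can speak about clinic needs, perceived value and their own limited involvement, which Sections 2.0, 4.0 and 8.0 want to learn. This stands too and is a reason to keep their interviews.

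**Conclusion.** The stated source is the wrong one for this component. Followed as written, it cannot yield the implementation cost of each arm that Section 6.0 requires. This rests on reading clinic staff as Sections 3.0, 4.0 and 5.0 define it.

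Two further inferences are tempting, and the documents do not support them. One is that the gap flatters the clinically integrated arm. The set-up cost of the peer arm is missed by the same interviews, so the direction is unknown. The other is to express the omission as a share of coaching time. Scheduled visits come to 60 + 2 × 20 = 100 up to 90 + 2 × 45 = 180 minutes per patient. But patients are offered up to three visits and may attend fewer, and messaging and moderation come on top. No training, set-up or supervision hours are given to set against that total, so any percentage would reflect only the hours assumed.

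The per-patient implementation cost therefore lacks an informed source in both supported arms. The effect on any ICER that includes it has unknown size and sign.

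**What to change.** - In Section 6.0 and Table 1, name the planned month-36 interviews with health coaches, peer mentors and their organisations' decision makers as the source of implementation cost for both supported arms.
- Add items to those interviews on hours spent on training, set-up, supervision and discussion moderation. Record training needed only for the research, such as protocol procedures and human-subjects courses, separately so that it can be left out of implementation cost.
- Keep the primary care clinician interviews for clinic needs, perceived value and engagement, including limited involvement, but not as the source of implementation cost for the delivery arms.
- State in Section 8.0 whether the ICER includes implementation cost, and in Section 6.0 what counts as implementation cost in the self-monitoring group, which neither set of interviews covers.
- Reconcile the number of peer staff, given in Section 5.0 as two specialists in one place and four mentors in another, so that everyone who delivered the arm is asked.

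The price is a few extra items in interviews already scheduled, some recall error in hours reported at month 36, and possibly a higher stated cost for the supported arms.

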7.0 STUDY PARAMETERS

Patients will be block randomized by clinic, sex, and alcohol use severity to control for demographics at a 1:1:1 ratio to be in the self-monitoring, peer-supported Tula, or clinically integrated Tula groups. It's anticipated that 3-7 clinics (defined as having at least 10 patients in the study) with 3-7 clinicians each and 546 patient subjects will be recruited from the participating UW Health clinics. Patients will have access to Tula for up to 48 months, depending on time of enrollment, although the active period of participation is defined as 3 months with follow up through 12 months post enrollment (9 month follow-up). Health coaches will have access to patient-shared Tula data from patients of the clinically integrated Tula group for the duration of the study. The peer mentor will have access to discussion boards and private messages on Tula for the duration of the study for patients in the peer-supported

Protocol
HS IRB #2019-0337
Version 5. 10/17/19
Version 6. 04/07/20
Version 7. 10/09/20
Version 8. 01/26/21
Version 9. 08/18/21
Version 10. 07/13/23

group. The research team will have access to all Tula data for all subjects in all groups for the duration of the study.

